Provide enough relevant information to allow the IRB reviewers to understand the rationale and/or justification for the study and its merits (basic and/or applied), including any relevant study hypotheses and dissemination plans.

Presbyopia is an ocular condition resulting from the reduced flexibility and consequent loss of accommodation, an ability to change the optical power of the human crystalline lens. It results in a limited range of focal distances for forming a clear retinal image. The typical clinical solution to presbyopia is the fitting of single-vision or multifocal spectacle lenses. Alternatively, single- and multi-focal contact lens can be fitted for presbyopes who can adapt to contact lens wearing. Multi-focal lenses provide the convenience of changing focal distances with a single lens; however, unwanted aberrations due to transition between optical zones for different focal distances can be a significant compromise with these solutions.

OneFocus Vision, Inc. (OFV) has previously bench-tested a proprietary design of accommodative contact lens (ACL), and would like to contract the Vision Performance Institute for a non-dispensing (within-laboratory wearing only) clinical test. This novel design of ACL is based on the interaction between the force exerted by the lower eyelid and the fluid (saline or contact lens solution) inside a cavity within the contact lens. The cavity exists within the lens between two layers of hydrogel, and does not get in touch with the corneal surface. The water-absorbing/peameating hydrogel also allows the cavity to be filled with fluid. When the lens is stored in saline or in lens care solution, the cavity will be filled with saline or lens care solution respectively. When it is taken out of the storage box and worn over the eye during the testing, the saline or lens care solution should mostly remain in the cavity, and some (if any) tears might be absorbed into the cavity. OFV bench tests have shown that when micro-pressure (from the lower lid) is applied to the surface above the reservoir(s) containing the fluid, the fluid is pushed through channel(s) and enters a large reservoir extending throughout the optical zone that covers the pupil. Such action in turn changes the optical power of the contact lens that covers the pupil of the eye.

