Four sites will be involved in the study:

1. VPI: The study will be conducted in [name] at the Forest Grove campus. [name] will conduct the vision screening and lens testing.
2. Salem clinic: Testing will be conducted at [name]. [name] will conduct the vision screening and lens testing.
3. San Diego clinic: Testing will be conducted at [name]. [name] will conduct vision screening and lens testing.
4. New York clinic: Testing will be conducted at [name]. [name] will conduct the vision screening and lens testing.

2. Study Materials, Measures, and/or Apparatus to be Applied

- Test lens: Contact lenses manufactured with standard soft contact lens material, hydrogel, will be tested (see Technical Description of Test Lens). Based on the FDA procedure for classifying medical devices, the test lens should have an expected rating as a Class II, 510K device: proposed identifier 886.5925; product code, LPL (see FDA Device Regulation Guidance at <http://www.fda.gov/MedicalDevices/DeviceRegulationandGuidance/GuidanceDocuments/ucm080735.htm>). The test lens' biological compatibility also meets the FDA testing guidance, as demonstrated by the provided ocular irritation and toxicity reports for soft contact lens (see Ocular Irritation and Toxicity Reports)
- Video image of test lens: Infra-red video camera will be used to record the position of test lens in relation to the edge of pupil and lower eyelid.
- Corneal and test lens profile Image: Ocular coherence topography (OCT) will be taken with Zeiss Cirrus OCT (VPI) or similar anterior segment OCT (Co-investigational sites). Corneal and lens topography will be taken with the Medmont Topography System (VPI) or similar corneal topographer (Co-investigational sites) The OCT and topographer data will be used to visualize the position and shape of the test lens relative to the corneal surface.
- Measure of lens refraction power: Shin Nippon SRW-5500 Open Field Autorefractor (VPI) or other clinical autorefractor (Co-investigational sites) will be used to measure the refractive power and pupil size at different distances and downward angles with and without the test lens.

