- Visual acuity testing: An M&S visual acuity testing system (VPI) or similar computerized visual acuity testing system (Co-investigational sites) will be used to display high (95%) and low-contrast (10%) Snellen letters at distance (6 meters), intermediate (75 cm) and near (40 cm) testing distances.

3. Procedures

- Telephone Interview

Each participant will first talk to the optometrist who will determine whether they meet the recruiting criteria. If they meet the criteria, an appointment for the vision exam session will be scheduled.

- Visions Exam Session

During the vision exam session, they will first read, question and sign the consent form. They are now formally enrolled in the study and will then be examined by an optometrist (Drs. [name], [name], [name] or [name]). Distant monocular acuity, distance phoria, and accommodative amplitude will be measured. Additional refractive examinations will be conducted to ensure his/her eligibility. The participant will also be screened for any ocular diseases listed in the exclusion criteria. This will take about 45 to 60 minutes. Participants meeting the screening criteria will be invited back for the lens testing session. The second testing session can be scheduled immediately after the vision exam session or on a subsequent date, if it is more convenient for the patient. In the event that the participant chooses to return on a subsequent date, the optometrist will verbally re-consent the participant before the session begins.

- Testing

The formal testing session will last about 2 hours. At the beginning of the session, corneal topography will be taken without the test lens. The participant will then put on the test lens and corneal topography and corneal ocular coherence topography (OCT) will be taken while s/he views with 0, 15, and 25 degrees of downward angle. The viewing angle is enforced with a forehead/chin rest.

In the second task, participants will be asked to view an eye chart with the 3 downward angles (0, 15, and 25 degrees) and 6m, 75cm, and 40cm distances while their optical refraction is measured with a power refractor. The measured results are then compared to the accommodative demand at these 3 distances.

In the third task, eye charts will be presented at the 3 distances and corresponding angles (6 m for 0 degree, 75 cm for 15 degree, 40 cm for 25 degree)

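### The second task compares refraction only with a demand set by viewing distance, although the lens is driven by lid pressure in downgaze; an angle-by-lens contrast would test lens function better

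*Protocol*

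**What the plan says.** The Purpose section of the protocol describes a lens that works through the "interaction between the force exerted by the lower eyelid and the fluid (saline or contact lens solution) inside a cavity within the contact lens". Of the fluid movement that lid pressure causes, it says: "Such action in turn changes the optical power of the contact lens that covers the pupil of the eye". It gives no expected power for any gaze angle. The same section sets two aims: to confirm that the lens functions, and to measure the visual performance it affords.

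Under Study Methodology, 3. Procedures (Testing), participants in the second task "view an eye chart with the 3 downward angles (0, 15, and 25 degrees) and 6m, 75cm, and 40cm distances" while refraction is measured. One comparison follows: "The measured results are then compared to the accommodative demand at these 3 distances". The third task, by contrast, ties each distance to one angle: "6 m for 0 degree, 75 cm for 15 degree, 40 cm for 25 degree".

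Under Study Methodology, 2. Study Materials, the autorefractor is to "measure the refractive power and pupil size at different distances and downward angles with and without the test lens". The description of the second task does not take up the lens-off readings. The lens goes on in the first task and comes off after the fourth, so the session order does not show when those readings are made.

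**The concern.** The comparator is indexed by one factor (distance) and the mechanism by another (lid pressure, and so presumably gaze angle). Closeness to demand therefore mixes two questions: whether the lens changes power when the gaze drops, and whether the resulting power suits the target being viewed. For the first question, the informative contrast is the change with angle at a fixed distance, set against the same eye without the lens. The second task appears to collect what is needed, but does not name that contrast.

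Entry starts at age 40. Accommodative amplitude is measured at the vision exam but no limit is set on it. An eye that can still accommodate may meet the demand whether or not the lens does anything. What is at stake is whether the refraction data can support the aim of confirming lens function.

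**Working it through.** The protocol gives no figure for this comparison, so there is none to reproduce.

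**Inputs.** The distances (6 m, 0.75 m, 0.40 m), the angles (0, 15, 25 degrees) and the matched pairs come from the Testing section. The following are assumptions:
- Angle and distance are fully crossed.
- The working lens delivers, at each angle, the demand of the matched distance.
- The inert lens, and the eye without a lens, stay focused at 6 m.
- At first, the eye has no residual accommodation.

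**Demand** = 1/distance: 1/6 = 0.17 D, 1/0.75 = 1.33 D, 1/0.40 = 2.50 D. Adjacent steps are 1.17 D and the full step is 2.33 D.

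**Deviation** = power delivered minus demand, in dioptres, working lens / inert lens:

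| Downward angle | 6 m | 75 cm | 40 cm |
|---|---|---|---|
| 0° | 0.00 / 0.00 | −1.17 / −1.17 | −2.33 / −2.33 |
| 15° | +1.17 / 0.00 | 0.00 / −1.17 | −1.17 / −2.33 |
| 25° | +2.33 / 0.00 | +1.17 / −1.17 | 0.00 / −2.33 |

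Each lens departs from demand in six of nine cells. Mean absolute deviation:
- Working: (4 × 1.167 + 2 × 2.333)/9 = 1.04 D.
- Inert: (3 × 0 + 3 × 1.167 + 3 × 2.333)/9 = 1.17 D. If the inert eye and lens rest at 0 D instead, it is 1.33 D.

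The slope of refraction on distance demand is 0 for both lenses. The mean signed deviation does differ: 0.00 D working, −1.17 D inert.

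**Residual accommodation.** Suppose the eye can add up to A dioptres to make up a shortfall but cannot remove an excess. A is not in the documents, so a range is shown. Cells count as off when they differ from demand by more than 0.25 D (also an assumption; 0.50 D gives the same counts).

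| A (D) | Cells off, working / inert | Mean absolute deviation over nine cells, working / inert (D) | Inert lens, three matched cells only (D) |
|---|---|---|---|
| 0 | 6 / 6 | 1.04 / 1.17 | 1.17 |
| 0.5 | 6 / 6 | 0.87 / 0.83 | 0.83 |
| 1.0 | 4 / 3 | 0.70 / 0.50 | 0.50 |
| 1.5 | 4 / 3 | 0.61 / 0.28 | 0.28 |
| 2.5 | 3 / 0 | 0.52 / 0.00 | 0.00 |

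From 0.5 D upwards the inert lens has the smaller pooled deviation. In the matched cells the working lens is at 0.00 D throughout, and the inert lens approaches it as A rises.

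**Proposed contrast:** (with lens − without lens) at 25° minus (with − without) at 0°, same distance.
- At 6 m: working (2.50 − 0.17) − (0.17 − 0.17) = 2.33 D; inert 0 D. A does not enter, because there is no shortfall to make up at 6 m.
- At 40 cm, working lens, A = 1.0: lens-off refraction is 0.17 + 1.00 = 1.17 D at both angles, and lens-on is 1.17 D at 0° and 2.50 D at 25°. The contrast is (2.50 − 1.17) − (1.17 − 1.17) = 1.33 D.
- At 40 cm, A = 2.5: every reading is 2.50 D and the contrast is 0.

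This is why 6 m should lead. The corresponding 0-to-15° contrast at 6 m is 1.33 − 0.17 = 1.17 D.

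**The case against.** A reader might infer that the plan marks a working lens as wrong, or that its data cannot tell a working lens from an inert one. The documents do not support either. The protocol says only that results are compared with demand; it sets no tolerance, no pass rule and no pooling over cells. Read cell by cell, the two lenses separate at once: at 40 cm and 25° the deviation is 0.00 D for the working lens and −2.33 D for the inert one. The lens-off readings listed under Study Materials are a further control. The near-equality of 1.04 and 1.17 D belongs to a pooled summary that the plan does not prescribe.

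Full crossing is also inferred. The second task lists angles and distances in the order in which the third task pairs them. On a paired reading the working lens misses none of three cells. That removes the six-of-nine result but not the attribution problem, because angle and distance then move together and an accommodating eye can meet the demand unaided. That downgaze supplies the lid pressure is likewise a fair inference, not a statement.

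Comparison with demand also answers a proper question. If the lens adds power at 6 m in downgaze, the wearer is defocused there, and that is a real performance result. All nine cells are therefore worth keeping. Topography, OCT and video across the same angles also bear on function. These objections stand, and they limit the point to a better choice of contrast.

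**Conclusion.** The point holds in a limited form. The one comparison stated for the second task is indexed by distance, whereas lens power is tied to lid pressure. On the crossed reading with no residual accommodation, a lens delivering the matched power at each angle deviates from demand in six of nine cells, with a pooled deviation close to an inert lens's. With 0.5 to 2.5 D of assumed residual accommodation, the pooled deviation favours the inert lens. On either reading, agreement with demand alone cannot be attributed to the lens.

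The sizes rest on an idealised lens and on assumed accommodation, because the protocol gives neither power per angle nor any limit on amplitude. This is worth changing but is not a must-fix: the study is a within-laboratory feasibility study, the second task is not named as primary, and the type of data needed is already planned.

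**What to change.** In the Testing section, second task:

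1. State whether the three angles and three distances are crossed.
2. Name as the measure of lens function the within-eye difference in refraction with and without the lens, compared between 0 and 15 degrees and between 0 and 25 degrees at the same distance, with 6 m as the lead row. A lens-on contrast alone would credit the lens with any gaze-related change in the eye itself.
3. Say when in the session the lens-off readings at each angle and distance are taken.
4. Keep the comparison with accommodative demand as a visual-performance result, reported by cell, with 6 m/0°, 75 cm/15° and 40 cm/25° marked as the intended-use conditions.

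The cost is a few sentences. No new type of measurement, visit or participant is needed. If only the three pairs were intended, the lead contrast also needs readings at 6 m at 15 and 25 degrees, with and without the lens.
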